3.5.2 Immunogenicity Analysis Populations

Per Protocol Immunogenicity (PPI)

The PPI population will serve as the primary population for the evaluation of immunogenicity. To be eligible for inclusion in the PPI population, randomized study participants must satisfy the following criteria:

- Eligible to be included in the PPE population as defined in Section 3.5.1;
- Have provided serum sample for NAb and IgG ELISA evaluation at 1 month post last dose (Month 7) within the visit window specified in the SoA (i.e., 21 to 49 days after dose 3 of V160 or placebo).

3.5.3 Safety Analysis Population

All Participants as Treated (APaT)

The APaT population will serve as the primary population for evaluation of safety. The APaT population includes all randomized participants who received at least 1 injection of V160 or placebo, have safety follow-up data, and assigns participants to the treatment arm corresponding to the actual clinical material received. For participants who received injections of V160 or placebo corresponding to a sequence that does not correspond to any of the protocol-defined treatment arms (ie, cross-treated participants), a safety profile listing will be created separate from the safety reports that will be provided for the protocol-defined treatment arms.

3.6 Statistical Methods

Statistical testing and inference relating to efficacy are described in Section 3.6.1. Statistical methods relating to safety analyses are described in Section 3.6.3. Efficacy results that will be deemed to be statistically significant after consideration of the Type 1 error control strategy are described in Section 3.8. Nominal p-values may be computed for other efficacy analyses, but should be interpreted with caution due to potential issues of multiplicity, sample size, etc. Unless otherwise stated, all statistical tests will be conducted at the $\alpha=0.025$ (1-sided) level.

3.6.1 Statistical Methods for Efficacy Analyses

To address the primary and secondary efficacy hypotheses, one-sided tests of the null hypothesis that the vaccine efficacy is 0% versus the alternative that vaccine efficacy is >0% will be conducted separately for each of the primary and secondary hypotheses. Each of the primary and secondary efficacy hypotheses will be tested at one-sided $\alpha=0.025$ level (ie, 2.5% Type 1 error). Vaccine efficacy is defined as:

$$VE = 100\% * \{1 - (R_v/R_p)\}$$

where R_v and R_p are the incidence rates CMVi in the V160 dose regimen (3-dose for the primary efficacy hypothesis testing; 2-dose for the secondary efficacy hypothesis testing) and placebo groups, respectively. The incidence rate R_v is defined as $R_v = C_v/T_v$, where C_v = the count of CMVi cases in the vaccine group and T_v = total person-years of follow-up for efficacy in the vaccine group. The incidence rate R_p is defined similarly. The null hypothesis that vaccine is not efficacious (ie, $VE=0\%$) will be tested by constructing a $100*(1-\alpha)\%$ confidence interval (CI) for VE, denoted as (VE_L, VE_U) , based on study data at a particular analysis time point (eg, at IA or at final analysis). The statistical criterion for success with respect to the primary efficacy hypothesis (and likewise for the secondary efficacy hypothesis) will be met if $VE_L > 0\%$.

The $100*(1-\alpha)\%$ CI for VE, (VE_L, VE_U) , is constructed as follows. Under the assumption that R_v and R_p are the means of independent Poisson processes, and given that there is a total of $n = C_v + C_p$ efficacy endpoint cases observed in the combined V160 dose regimen and placebo groups, then the number of primary efficacy cases C_v in the V160 dose regimen group is distributed as Binomial(n, π), where the binomial probability π is defined as $\pi = T_v R_v / (T_v R_v + T_p R_p)$. The probability π is a person-years-adjusted estimate of the probability

that a particular study participant who became a case of CMVi belongs to the V160 dose regimen group. The lower bound of the $100*(1-\alpha)$ % exact CI for the probability π is obtained by searching for the proportion π_L such that the probability of observing C_v or more efficacy endpoint cases out of n total efficacy cases is $\leq \alpha/2$. Similarly, the upper bound of the $100*(1-\alpha)$ % exact CI for the probability π is obtained by searching for the proportion π_U such that the probability of observing C_v or fewer efficacy endpoint cases out of n total efficacy cases is $\leq \alpha/2$ [1]. VE_L and VE_U are then calculated from π_L and π_U as follows:

$$VE_L = 100\% * \{1 - \pi_U (1+\theta)\} / (1 - \pi_U);$$
$$VE_U = 100\% * \{1 - \pi_L (1+\theta)\} / (1 - \pi_L);$$

where $\theta = T_p/T_v$ is the ratio of the total person-years of follow-up for efficacy in the placebo group over the V160 dose regimen group.

There is only one final analysis of the secondary efficacy endpoint. However, the testing of the secondary efficacy hypothesis may occur at the time of the IA or the final analysis of the primary efficacy hypothesis. The secondary efficacy hypothesis will only be tested if the primary efficacy hypothesis is successfully demonstrated. In addition, the secondary efficacy hypothesis will be tested contingent on accumulation of ≥ 15 total CMVi cases in the V160 2-dose and placebo regimens (see [Figure 1](#) in Section 3.7, and Section 3.9.2). Thus, the possible timing for testing the secondary hypothesis is as follows.

- If the primary hypothesis test is successful at the IA *and* there are ≥ 15 total CMVi cases in the V160 2-dose and placebo regimens at the time of IA, then the secondary efficacy hypothesis will be tested immediately after the testing of the primary efficacy hypothesis at the time of the IA.
- If the primary hypothesis test is successful at the IA and there are < 15 total CMVi cases in the V160 2-dose and placebo regimens at the time of IA, the secondary efficacy hypothesis will not be tested at the IA. In this case, follow-up will continue until at least 15 total CMVi cases in the V160 2-dose and placebo regimens groups are accrued. Upon accrual of ≥ 15 total CMVi cases in the V160 2-dose and placebo regimens, the secondary efficacy hypothesis will be tested.
- If the primary hypothesis test is not successful at the IA, the secondary efficacy hypothesis will not be tested at the time of the IA.

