| 
 • Objective: To demonstrate the efficacy of a 3-dose regimen of V160 in reducing the incidence of primary CMVi during the follow-up period after the last dose of the vaccine 
 • Hypothesis 1: Administration of a 3-dose regimen of V160 will reduce the incidence of primary CMVi compared to placebo. (The statistical criterion for success requires the lower limit of the 95% CI of VE to be greater than 0%) • Objective: To assess the safety and tolerability of a 2-dose and a 3-dose regimen of V160 | 
 • Incidence of CMVi in the 3-dose vaccine and placebo groups during the follow-up period after the last dose of a 3-dose regimen of the vaccine • Number of participants in the 2-dose and 3-dose vaccine groups experiencing solicited injection site AEs within Days 1 through 5 after each vaccination visit; solicited systemic AEs; and vaccine-related SAEs within Days 1 through 14 after each vaccination visit |
| Secondary | |
| 
 • Objective: To demonstrate the efficacy of a 2-dose regimen of V160 in reducing the incidence of primary CMVi during the follow-up period after the last dose of the vaccine 
 • Hypothesis 2: Administration of a 2-dose regimen of V160 will reduce the incidence of primary CMVi compared to placebo. (The statistical criterion for success requires the lower limit of the 95% CI of VE to be greater than 0%). | 
 • Incidence of CMVi in the 2-dose vaccine and placebo groups during the follow-up period after the last dose of a 2-dose regimen of the vaccine |

| Objective/Hypothesis | Endpoint |

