10.6.1 Statistical Methods for Efficacy Analyses

To address the primary and secondary efficacy hypotheses, one-sided tests of the null hypothesis that the vaccine efficacy is 0% versus the alternative that vaccine efficacy is >0% will be conducted separately for each of the primary and secondary hypotheses. Each of the primary and secondary efficacy hypotheses will be tested at one-sided $\alpha=0.025$ level (ie, 2.5% Type 1 error). Vaccine efficacy is defined as:

$$VE = 100\% * \{1 - (R_v/R_p)\}$$

where R_v and R_p are the incidence rates CMVi in the V160 dose regimen (3-dose for the primary efficacy hypothesis testing; 2-dose for the secondary efficacy hypothesis testing) and placebo groups, respectively. The incidence rate R_v is defined as $R_v = C_v/T_v$, where C_v = the count of CMVi cases in the vaccine group and T_v = total person-years of follow-up for efficacy in the vaccine group. The incidence rate R_p is defined similarly. The null hypothesis that vaccine is not efficacious (ie, $VE=0\%$) will be tested by constructing a $100*(1-\alpha)\%$ confidence interval (CI) for VE, denoted as (VE_L, VE_U) , based on study data at a particular analysis time point (eg, at IA or at final analysis). The statistical criterion for success with respect to the primary efficacy hypothesis (and likewise for the secondary efficacy hypothesis) will be met if $VE_L > 0\%$.

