|------------------------------------------------------|---------------------------------------------------------------------------------------------------------------------------------------------------------------------------------------------------------------------------------------------------------------------------------------------------------------------------------------------------------------------------------------------------------------------------------------------------------------------------------------------------------------------------------------------------------------------------------------------------------------------------------------------------------------------------------------------------------------------------------------------------------------------------------------------------------------------|
| Analysis Populations | Efficacy: Per-Protocol Efficacy (PPE) Safety: All Participants as Treated (APaT) |
| Primary Endpoint(s) | 
 Efficacy: number of participants with CMVi in the V160 3-dose regimen and placebo arms. Safety: number of participants experiencing solicited injection site AEs within Days 1 through 5 after each vaccination visit; solicited systemic AEs and vaccine-related serious AEs within Days 1 through 14 after each vaccination visit. |
| Key Secondary Endpoints | Efficacy: number of participants with CMVi in the V160 2-dose regimen and placebo arms. |
| Statistical Methods for Key Efficacy Analyses | The primary and secondary efficacy hypotheses will be evaluated by calculating the efficacy of V160 compared to placebo with respect to the CMVi endpoint. The p-value for testing the hypothesis that VE>0% as well as estimation of the 95% CI of VE will be based on the exact binomial method proposed by Chan and Bohidar [1]. |

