3.8 Multiplicity

The overall 1-sided Type 1 error in testing the efficacy hypotheses is controlled to not exceed 2.5% based on gatekeeping procedure.

The primary efficacy hypothesis will be tested at an overall (over the IA and final analysis) 1-sided Type 1 error $<2.5\%$, as discussed in Section 3.9.1. The secondary efficacy hypothesis will be tested at 1-sided Type 1 error $\leq 2.5\%$ only if the primary efficacy hypothesis is successfully demonstrated, as discussed in Section 3.9.2. The primary efficacy hypothesis is a reasonable gatekeeper to the secondary efficacy hypothesis because if a V160 3-dose regimen with last dose at Month 6 is not efficacious, then a V160 2-dose regimen with last dose also at Month 6 is highly unlikely to be efficacious.

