3.9 Sample Size and Power Calculations

3.9.1 Sample Size and Power for Efficacy Analyses

3.9.1.1 Sample Size and Power for Testing the Primary Efficacy Hypothesis

The power corresponding to the decision rule that will be implemented in testing the primary efficacy hypothesis is based on a fixed-event design. For testing the primary efficacy hypothesis, participants will be followed until 15 total CMVi cases in the combined V160 3-dose and placebo regimens have been accumulated, at which point, an IA will be conducted. If the testing of the primary efficacy hypothesis is inconclusive at the IA, follow-up will continue until 24 total CMVi cases have been observed in the combined V160 3-dose and placebo regimens. The decision rules to be implemented that will determine success or failure to demonstrate the primary efficacy hypothesis are as shown in [Figure 1](#) in Section 3.7 and in [Table 2](#). Corresponding to these decision rules, the study has $>90\%$ power to demonstrate that the efficacy of a V160 3-dose regimen compared to placebo to prevent CMVi is $>0\%$ if the underlying vaccine efficacy is $\geq 80\%$ at an overall one-sided Type 1 error equal to 2.3%. The operating characteristics of the decision rules with one IA and a final analysis if necessary are evaluated by a 5 million-replication simulation using SAS v9.4. In the simulation conducted, the underlying probability distribution of accumulation of CMVi cases in the V160 3-dose regimen conditional on the total cases in the combined V160 and placebo regimens is based on an exact method under a large sample Poisson distribution assumption proposed by Chan and Bohidar (1998) [1].

This study will randomize 700 participants into the V160 3-dose regimen and 700 into the placebo regimen. The 15 total CMVi cases in the combined V160 3-dose and placebo regimens are projected to be accumulated in ≈ 18 to 19 months under the following assumptions: 1) all 1,400 participants are enrolled within 18 months; 2) incidence of CMVi in the placebo group is 2% per year; 2) VE=85%, so that the incidence of CMVi in the V160 arm is 0.3% per year; 3) loss-to-follow-up is $\approx 5\%$ to 10% per year; and 4) participants ineligible for the PPE analysis is $\approx 2\%$ to 5% of participants randomized. Under the same assumptions, the total of 24 CMVi cases in the combined V160 3-dose and placebo regimens is projected to be accumulated in ≈ 3 years.

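### The stated primary success rule (lower 95% CI limit of VE above 0% at each look) is not tied to the Table 2/3 case splits; at the 17-case interim they differ, and the CI rule has 3.1% one-sided error at equal person-time

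*Combined protocol and SAP*

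**What the plan says.** Two statements of primary success stand side by side.

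**The CI rule.** Protocol 10.6.1 and sSAP 3.6.1 build the interval on data "at a particular analysis time point (eg, at IA or at final analysis") and continue: "The statistical criterion for success with respect to the primary efficacy hypothesis (and likewise for the secondary efficacy hypothesis) will be met if" VE_L is above 0%. Neither sentence names a case boundary or an adjusted level. Protocol Section 4 attaches this to the hypothesis, in per cent: "The statistical criterion for success requires the lower limit of the 95% CI of VE to be greater than 0". sSAP 3.1 says that "estimation of the 95% CI of VE will be based on the exact binomial method". The interval uses observed person-time through theta, which "is the ratio of the total person-years of follow-up for efficacy in the placebo group over the V160 dose regimen group".

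**The count rule.** sSAP 3.9.1.1 states: "The decision rules to be implemented that will determine success or failure to demonstrate the primary efficacy hypothesis are as shown in" Figure 1 and Table 2. For an interim at 17 cases, Table 2 gives success at 3 or fewer vaccine cases, futility at 8 or more, and a final at 26 cases with success at 7 or fewer. Table 3 extends the final to 35 cases.

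**The links between them.** sSAP 3.6: "Efficacy results that will be deemed to be statistically significant after consideration of the Type 1 error control strategy are described in Section 3.8". sSAP 3.8: "The overall 1-sided Type 1 error in testing the efficacy hypotheses is controlled to not exceed 2.5% based on gatekeeping procedure"; it then refers to 3.9.1 for the primary test. Footnote a to Tables 2 and 3 promises a multiplicity-adjusted p-value and CI, but 3.6.1 does not make these the criterion.

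**The concern.** An unadjusted 95% lower limit used as the success criterion at two looks spends close to 2.5% at each look if the discreteness of the counts allows it. Nothing in that rule holds the total to 2.5%. The tabulated splits do hold it, at equal person-time. If the two rules always gave the same answer, the duplication would be harmless.

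They do not. The documents' own tables show the clash: sSAP Table 4 prints a lower limit of 0.4% for 4:13, which is above 0%, while Table 2 asks for 3 or fewer of 17. The interim was held at 17 cases. A 4-of-17 result was not remote: its probability is 22% at VE 70% and 17% at VE 80%.

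The final test may also still be needed, since sSAP 3.9.1.1 says the blinded team does not know whether the interim succeeded or was inconclusive. The same data could then be a success under one section and a failure under another.

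**Working it through.** **Inputs.** Allocation 700 to 700, interim at 17 cases, and the Table 2 and 3 boundaries (sSAP 3.9.1.1); 95% exact binomial CI (protocol Section 4, sSAP 3.1); cap of 2.5% one-sided (sSAP 3.8). Theta is not given. I take theta = 1 first, then vary it, using one theta for both looks.

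**Formulas.** Given the total number of cases, vaccine cases are binomial with pi = (1 − VE)/((1 − VE) + theta), so under the null pi = 1/(1 + theta). The sSAP limit equals VE_L = 1 − theta × pi_U/(1 − pi_U). Two-look error = P(X17 ≤ s1) + Σ P(X17 = x) × P(X9 ≤ 7 − x) over x > s1, for a final at 26.

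**1. Reproduce Table 2, 17-case row (3 of 17, then 7 of 26; pi = 0.5).**
- P(X17 ≤ 3) = 0.006363
- x = 4: 0.01816 × 0.25391 = 0.004610
- x = 5: 0.04721 × 0.08984 = 0.004242
- x = 6: 0.09442 × 0.01953 = 0.001844
- x = 7: 0.14838 × 0.00195 = 0.000290
- Total: 0.006363 + 0.010986 = 0.01735

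This matches the printed 0.6% and 1.7%. Power at the final is 77.3% (VE 70%) and 94.7% (VE 80%), also as printed.

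**2. CI rule at 17 cases.** For 4 of 17, pi_U = 0.49899, so VE_L = 1 − 0.49899/0.50101 = +0.4%. The point estimate is 1 − 4/13 = 69.2% and the upper limit 92.7%. The CI rule therefore accepts 4 or fewer. At 26 cases it accepts 7 or fewer, as Table 2 does.

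**3. Error of the CI rule at both looks.** P(X17 ≤ 4) = 0.02452. Adding 0.004242 + 0.001844 + 0.000290 = 0.006376 gives 0.0309, or 3.09%. For finals at 26 to 35 the range is 2.83% to 3.78%, against 1.32% to 2.43% for the tabulated splits.

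**4. Other interim counts.** At 15, 16 and 18 to 22 cases the two rules coincide, with errors of 2.34, 2.05, 2.31, 1.86, 2.36, 2.34 and 1.56%.

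**5. Sensitivity of the interim result to theta (final at 26).** The 4:13 lower limit reaches 0 at theta 1.0040. At 1.005 the CI rule accepts only 3 of 17 and its error is 1.79%. At 0.95 it still accepts 4 of 17, and its error is 2.37%.

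**6. Final analysis.** At theta = 1 the rules agree at every count from 26 to 35. Away from 1, with the interim decided at 3 of 17:

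| Final cases | theta | Split | 95% lower limit | Table 3 success | Cumulative error if this split is accepted |
|---|---|---|---|---|---|
| 32 | 0.999 | 10:22 | +0.07% | 9 or fewer | 0.633% + 2.148% = 2.78% |
| 27 | 0.99 | 8:19 | +0.28% | 7 or fewer | 0.601% + 2.063% = 2.66% |
| 30 | 1.03 | 9:21 | −0.54% | 9 or fewer | 0.752% + 2.163% = 2.91% |

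In the first two rows the CI rule accepts what Table 3 rejects. In the third it rejects what Table 3 accepts, and the 2.91% belongs to the tabulated count.

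**7. Alpha notation.** 3.6.1 sets alpha = 0.025 one-sided, then writes a 100(1 − alpha)% interval with alpha/2 per tail. Read literally that is a 97.5% interval. It gives 3 of 17 and 6 of 26 (Table 2: 3 and 7), and 2 of 15 (Table 2: 3).

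**8. Misprint.** The 17-case row of protocol Table 7 and sSAP Table 4 prints VE 79.2% for 4:13; 1 − 4/13 = 69.2%.

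**The case against.** The best reply is that the tables already govern. sSAP 3.6 sends significance to 3.8, 3.8 sends it to 3.9.1, and 3.9.1.1 says that Tables 2 and 3 hold the rules to be applied. The sSAP's own change summary says Table 2 was expanded to fix the rules before the next case count. A careful reader would follow the tables, and most of this stands. What remains is that the sentence defining success in 3.6.1 and 10.6.1 does not point to the tables, and that no section says what happens when the person-time-based interval and a fixed count disagree.

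Three further points are fair:
- Section 4 words the lower limit as something required. It can be read as a necessary condition, which every tabulated boundary meets at theta = 1, and it names no look. A reader might infer that Section 4 alone breaches the cap; its wording does not go that far.
- 3.6.1 taken wholly literally, with its 97.5% interval, accepts only 3 of 17, so the interim conflict vanishes. The conflict needs the 95% level of Section 4 and sSAP 3.1. That is clearly the intended level, since the tables print 95% intervals and the literal one does not reproduce their boundaries.
- The 17-case look is complete. Footnote c to Table 3 records that it was run on the plan of a final at 26 cases, with futility at 8 or more.

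**Conclusion.** The stated criterion is wrong as written and should be corrected. At the 95% level and equal person-time, applying it at both looks gives 3.09% one-sided error at the interim count actually used (2.83% to 3.78% over finals at 26 to 35), above the 2.5% cap. At the final, imbalances of 0.1% to 1% in person-time are enough for it to accept a split that Table 3 rejects, with cumulative error of 2.66% to 2.78%.

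A reader might infer that the trial's design fails to control error. The documents do not support that: at equal person-time the tabulated rule has 1.73% with the final at 26, and at most 2.43% up to 35 cases. Nor do they show that 4:13 was observed or that the interim was misjudged. They report only 17 total cases, that futility was not met, and a recommendation to continue.

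The sizes rest on an assumed theta. At 17 cases the conflict disappears above theta 1.0040. The tabulated error rates also depend on theta (2.91% at 30 cases and theta 1.03). That calls for disclosure, not for a new boundary after the interim.

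**What to change.** Before the final case count:
- In protocol 10.6.1 and sSAP 3.6.1, with a matching note in Section 4 and sSAP 3.1, state that primary success at each look is decided by the vaccine-case boundaries in sSAP Tables 2 and 3. State that the unadjusted 95% CI of VE is descriptive for the primary hypothesis, and that the group-sequential adjusted CI and p-value of footnote a are reported.
- Write the interval as two-sided 95% with 0.025 per tail.
- Note in the sSAP that the tabulated error rates assume equal person-time, and report the cumulative error at the observed theta. No theta-dependent boundary is needed.
- Correct 79.2 to 69.2 in the 17-case row of protocol Table 7 and sSAP Table 4.

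The cost is wording only, with no new data and no change to any tabulated boundary. Under sSAP Section 1, a change to the methods for a primary hypothesis needs a protocol amendment before unblinding. Power stays as tabulated. Compared with the CI rule at both looks (final at 26, theta = 1), success probability is 77.3% rather than 80.2% at VE 70%, and 94.7% rather than 95.5% at VE 80%.

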3.6.2 Statistical Methods for Immunogenicity Analyses

Within a vaccination group, GMT and the corresponding 95% CI will be derived by taking the anti-logarithm of the mean of the log-transformed antibody titers and its corresponding 95% CI (calculated based on the t-distribution). Antibody titers reported as less than the lower limit of quantitation (LLOQ) of the relevant assay will be replaced by the half of the LLOQ in the log-transformation of antibody titers.

Geometric mean concentration (GMC) of ELISPOT measures and the corresponding 95% CI will be calculated similar to the calculations of GMT and its corresponding 95% CI.

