| 
 To assess and compare the kinetics of humoral immune response induced by 2-dose and 3-dose regimens of V160 To assess and compare the kinetics of CMI response induced by 2-dose and 3-dose regimens of V160 in a subset of study participants^b To evaluate the incidence of cCMVi in infants born to recipients of 2-dose and 3-dose regimens of V160 compared to placebo, during the follow-up period after the last dose of vaccine or placebo To follow the outcomes of infants diagnosed with cCMVi in the study To explore potential correlations between humoral and CMI response to 2-dose and 3-dose regimens of V160 and efficacy of 2-dose and 3-dose regimens of V160 against CMVi | 
 Percent of participants who seroconvert based on the NAb and IgG ELISA assays from CMV seronegative at Day 1 to CMV seropositive at Month 7^a Seropositivity based on the NAb and IgG ELISA assays at Day 1, Months 6, 7^a, 12, 24, and 36 GMT based on the NAb and the IgG ELISA assays at Day 1, Months 6, 7^a, 12, 24, and 36 Geometric mean count (GMc) of spot forming cells (SFC) per million PBMCs (SFC/10⁶ PBMCs) based on the ELISPOT assay at Day 1, Months 6, 7^a, 12, 24 and 36 Incidence of cCMVi cases in the V160 2-dose, V160 3-dose, and placebo groups during the follow-up period after the last dose of vaccine or placebo Hearing, vision, and neurological outcomes of infants diagnosed with cCMVi over 3 years Immune responses in participants in the 2-dose and 3-dose vaccine groups with and without CMVi during the follow-up period after the last dose of V160 |

^a Month 7 is the time point corresponding to 1 month following last dose of the 2-dose and 3-dose regimen of V160

^b In Detailed Immunogenicity sub-study participants only (N≈360).

cCMVi = Congenital CMV infection; CMV = Cytomegalovirus; CMVi = CMV infection;

DNA = Deoxyribonucleic acid; ELISA = Enzyme-linked immunosorbent assay

ELISPOT = Enzyme-linked immunosorbent spot; IgG = Immunoglobulin G

NAb = Neutralizing antibody

PCR = Polymerase chain reaction; PBMC = Peripheral blood mononuclear cells

SFC = Spot forming cells

5. Study Design

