10.6.2 Statistical Methods for Immunogenicity Analyses

Statistical methods for analysis of exploratory immunogenicity endpoints will be provided in the sSAP that will be written for this study.

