2.2 Version 2.0

1. Section 3.4.2 no longer has the seroconversion and seropositivity immunogenicity endpoints. These endpoints cannot be defined because both the CMV-specific NAb assay and the IgG ELISA currently do not have identified seropositivity cutoffs that can be used to identify participants who are seropositive based on either of the two assays.

2. Section 3.5.2 provides the definition of the per-protocol immunogenicity (PPI) analysis population.
3. Section 3.6.2 provides the method that will be used in calculating geometric mean titers (GMTs) and the corresponding 95% confidence interval (CI) based on the CMV-specific neutralizing antibody (NAb) assay and IgG enzyme-linked immunosorbent assay (ELISA).
4. Section 3.9.1.1 has a new subsection (Final Testing of the Primary Efficacy Hypothesis) along with a new **Table 3** that provides the decision rules that will be applied in the event that a final testing of the primary efficacy hypothesis needs to be conducted at total primary efficacy endpoint case count that is greater than 26 in the combined V160 3-dose and placebo groups (conditional on the IA being conducted at 17 total cases in the combined V160 3-dose and placebo groups).
5. **Table 4** in Section 3.9.1.2 has been expanded to cover situations when the secondary efficacy hypothesis is tested at 25 or more (through 35 cases) total cases in the V160 2-dose and placebo groups.

3. Analytical and Methodological Details

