3.4.2 Immunogenicity Endpoints

All immunogenicity endpoints in this study are exploratory endpoints and are listed below.

- GMTs based on the NAb and the IgG ELISA assays at Day 1, Months 7, 12, 24, and 36.
- GMc of SFC/10⁶ PBMCs based on the ELISPOT assay Day 1, Months 6, 7, 12, and 24.

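### The exploratory objectives promise a 2-dose versus 3-dose comparison of immune kinetics, but the sSAP's immunogenicity methods stop at within-group summaries and specify no between-regimen contrast

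*Combined protocol and SAP*

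**What the plan says.** Protocol Section 4 states the humoral objective as "To assess and compare the kinetics of humoral immune response induced by 2-dose and 3-dose regimens of V160". The cell-mediated objective has the same form: "To assess and compare the kinetics of CMI response induced by 2-dose and 3-dose regimens of V160 in a subset of study participants".

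Protocol 10.6.2 contains no method: "Statistical methods for analysis of exploratory immunogenicity endpoints will be provided in the sSAP that will be written for this study".

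sSAP 3.6.2 is where the method then appears. For titres: "Within a vaccination group, GMT and the corresponding 95% CI will be derived by taking the anti-logarithm" of the mean log titre and its t-based interval, with values below the quantitation limit set to half that limit. For the sub-study assay: "Geometric mean concentration (GMC) of ELISPOT measures and the corresponding 95% CI will be calculated similar to the calculations of GMT". The sSAP's Version 2.0 change list (Section 2.2) describes 3.6.2 no more broadly, as the method for calculating GMTs and their 95% CIs.

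The visits come from sSAP 3.4.2. Serology is listed as "GMTs based on the NAb and the IgG ELISA assays at Day 1, Months 7, 12, 24, and 36", and ELISPOT at Day 1 and Months 6, 7, 12 and 24.

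sSAP 3.6 sets a general rule, "Unless otherwise stated, all statistical tests will be conducted at the" one-sided 0.025 level, but names no immunogenicity test to which it could apply. Its allowance for nominal p-values covers other efficacy analyses only.

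**The concern.** An objective to compare needs an estimand and an estimate that compare. Here the objective names two regimens and the method produces one number and one interval per arm. The objective also says kinetics, yet the method has no summary across visits.

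These are the only objectives in Section 4 that set the two regimens against each other. Both efficacy hypotheses, the congenital infection objective and the Tier 2 safety intervals all compare V160 with placebo. If the immunogenicity contrast is not specified, the plan contains no direct comparison of the regimens. Any ratio later reported would then be chosen (visits, model, handling of repeated samples) after the per-arm results could be seen.

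**Working it through.** The documents give no SD, target ratio, power or sample size for this comparison, so there is no figure to reproduce. The check is mainly one of setting the texts side by side.

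**1. Objective against method.**

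| Element | Protocol Section 4 | sSAP 3.6.2 |
|---|---|---|
| Humoral, 2-dose vs 3-dose | assess and compare | GMT and 95% CI per arm |
| CMI, 2-dose vs 3-dose | assess and compare | geometric mean and 95% CI per arm |
| Kinetics | requested for both | no model or summary over time |
| Between-regimen estimate | implied by the objective | none |

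At the sSAP-listed visits after vaccination starts, the objectives imply 2 serology assays × 4 visits = 8 contrasts, and ELISPOT contrasts at 4 visits (for each antigen readout reported). None is specified.

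**2. Is the omission a stated choice?** The sSAP handles two neighbouring cases differently. Tier 2 safety endpoints are not tested, yet sSAP 3.6.3 and its Table 1 still give a between-group difference with 95% CI. For vaccine-type viral shedding, sSAP 3.6.3 explicitly rules out treatment comparisons, including 3-dose against 2-dose. Section 3.6.2 neither gives a comparison nor rules one out.

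**3. What the planned tables would still allow.** For arm *j*, let *m_j* = log10(GMT_j) and let *h_j* be half the width of the CI on the log10 scale. Then

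- SE_j = h_j / t(0.975, n_j − 1)
- d = m_3dose − m_2dose, with SE_d = √(SE_3dose² + SE_2dose²)
- ratio = 10^d, with 95% CI 10^(d ± t × SE_d)

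So an unadjusted ratio at a single visit can be rebuilt. A repeated-measures analysis cannot, because per-arm summaries do not carry the within-person correlation across visits.

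**4. How precise the direct ratio would be.** With equal arms and a common log10 SD, the smallest observed ratio whose 95% CI excludes 1 is 10^(t(0.975, 2n − 2) × SD × √(2/n)). The SD is not in the documents; 0.3 to 0.7 is an assumed range. Inputs for n are 700 per arm with 5% ineligible for the per-protocol population (700 × 0.95 = 665; sSAP 3.9.1.1), and 120 per arm in the sub-study (protocol Table 2).

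Worked case, n = 665 and SD = 0.5: 1.962 × 0.5 × √(2/665) = 0.0538, and 10^0.0538 = 1.13.

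| n per arm | SD 0.3 | SD 0.5 | SD 0.7 |
|---|---|---|---|
| 665 (serology) | 1.08 | 1.13 | 1.19 |
| 120 (sub-study) | 1.19 | 1.34 | 1.51 |

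Both values of n are optimistic. The immunogenicity population also needs a Month 7 serum sample in window, numbers fall at later visits, and the sub-study may enrol fewer than 360.

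**5. Visits.** At Month 6 the sub-study blood is drawn before the third injection. At that point the 3-dose arm has had two V160 doses and the 2-dose arm one V160 dose and one placebo, so this visit isolates the extra priming dose. Protocol Section 4 lists Month 6 for serology, but sSAP 3.4.2 does not.

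**The case against.** The strongest reply is that these endpoints are declared exploratory, carry no hypothesis and no alpha, and lie outside the multiplicity strategy. Side-by-side GMTs with intervals are a recognised way to describe such data, and step 3 shows that little information is lost at any single visit. The 2-dose schedule is judged formally by Hypothesis 2 against placebo, with its own decision table, not by titres. All of this stands and limits the weight of the point. It does not remove the mismatch, because the objective says compare and the method does not.

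For ELISPOT the reply is stronger. Protocol 5.4.1.2 says the assay gave robust responses in Phase 1 but did not allow quantitative comparison between groups, and that it is used here to confirm CMI responses. That also stands as a caveat, although it sits uneasily with an objective to compare CMI kinetics.

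Two stronger readings are tempting and are not supported:

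- A reader might infer that the regimens will be compared by whether the two intervals overlap. With equal standard errors that would need a difference of 2 × 1.96 = 3.92 standard errors of one arm's mean, against 1.96 × √2 = 2.77 for a direct interval, or 41% more. No section states or implies such a rule, so this figure prices a procedure the sponsor has not proposed and is not counted here.
- A reader might infer that the titre contrast is the most precise evidence on whether two doses are enough. That assumes titre predicts protection. The plan treats the link as unknown and lists it only as something to explore.

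**Conclusion.** The point holds as a gap between objective and method. Protocol Section 4 promises a comparison of the two regimens, and sSAP 3.6.2 specifies nothing that compares them. It is a low-cost improvement, not a threat to the trial: no primary or secondary efficacy conclusion depends on it, and no error rate or power figure in the plan changes. No numerical penalty can be attached, because the plan states no rule for the comparison. The precision figures in the working show only what the added ratio could resolve, and they rest on an assumed SD and on near-complete samples.

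**What to change.** In sSAP 3.6.2, add the 3-dose/2-dose geometric mean ratio with 95% CI, estimated on log values either by a two-sample t-interval at each visit or by a repeated-measures model with arm, visit and their interaction:

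- neutralizing antibody and IgG ELISA at Months 7, 12, 24 and 36, and at Month 6 in the sub-study, with Month 6 added to sSAP 3.4.2 so that it agrees with protocol Section 4;
- ELISPOT in the sub-study at the sSAP-listed Months 6, 7, 12 and 24. Protocol Section 4 also lists Month 36 for ELISPOT, and the two lists should be reconciled.

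Label all of these as descriptive with no alpha. Beside the ELISPOT ratios, note the Phase 1 limitation from protocol 5.4.1.2.

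The cost is a small amount of extra analysis and a few table rows, with no new samples or visits. sSAP Section 1 already allows changes to exploratory analyses to be documented in the sSAP before unblinding or final lock. If that point has passed, the ratios can still be reported but should be identified as post hoc in the study report.
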